5.2 Secondary Efficacy Endpoints

Secondary endpoints will include percentage of patients prescribed each medication class (i.e. percentage on beta-blockers, percentage on ACE-I/ARB, percentage of ARNIs, percentage on SGLT2i, and percentage on MRAs), medication doses of each therapy, all at 30-days as well as post-implementation at 6 months; HF hospitalizations at each time point, 6-month mortality, referrals, cardiac procedures. Outcomes determined by review of medical, hospital, and billing records.

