	mEq/L], hyperkalemia [K >5.5 mEq/L], AKI [defined as Cr increase >0.5 from baseline], Hyponatremia [Na<130 mg/dl], volume overload [urgent clinic visit/ ER visits for lower extremity edema, dyspnea, with clinical evaluation consistent with volume overload], hypotension (SBP <90mmHg), bradycardia (HR <50 bpm). Outcomes determined by review of medical, hospital, and billing records.
OTHER EVALUATIONS	None
SAFETY EVALUATIONS	Adverse events (to include hypokalemia [K<3.0 mEq/L], hyperkalemia [K >5.5 mEq/L], AKI [defined as Cr increase >0.5 from baseline], Hyponatremia [Na<130 mg/dl], volume overload [urgent clinic visit/ ER visits for lower extremity edema, dyspnea, with clinical evaluation consistent with volume overload], hypotension (SBP <90mmHg), bradycardia (HR <50 bpm).
PLANNED INTERIM ANALYSES	At 30-days after implementation for cluster 1, we will evaluate for safety. Serious adverse events will be monitored by the research team on an ongoing basis throughout the study.
STATISTICS Primary Analysis Plan	To assess the effectiveness of our intervention, measurement of rates of GDMT, including each specific medication of ACE inhibitors, ARB, ARNI, beta-blockers, MRA, SGLT2 inhibitors will be performed at baseline, at each cross-over time point, and at the conclusion of 6 months after the implementation of the intervention. The main analysis of our stepped wedge design will be based on a logistic mixed-effects model which will contain a random intercept to account for between-cluster variability, a fixed effect parameter for time, and a group indicator variable for the treatment for each subject and time to capture treatment differences over time.
Rationale for Number of Subjects	We anticipate there is approximately 100 patients with HFrEF actively engaged in care at GIMC. Our goal to enroll all patients given ethical concerns with withholding implementation to all patients.

SECTION 1: BACKGROUND

Statement of Purpose:

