The reasons for underutilization of appropriate GDMT in HF are multifactorial. In the Indian Health Service, access to cardiology care is severely limited, and HF care is provided primarily by primary care providers. We surveyed primary providers at two Indian Health Service sites to identify the primary barriers to getting HFrEF patients on appropriate GDMT. The primary barriers identified were include lack of knowledge/comfort among providers about guidelines and appropriate management, clinical burden, time constraints during the visit. Given this we hypothesized that a model that identified HFrEF patients not on appropriate therapy, and initiated missing recommended therapy by the study team would be an effective way to improve HF quality of care and uptake of GDMT. In addition, given the rurality of the Navajo patients cared for at these two IHS sites, and the barriers to accessing care, we hypothesized that a telemonitoring model in which patients had GDMT initiation and uptitration at home, with home BP monitoring would be preferable.

We therefore, in discussion with community members and primary providers at two IHS sites in Navajo, designed a model to identify HFrEF patients cared for in the system, identify gaps in their therapy, and initiate appropriate therapy by the study team with home BP and HR monitoring for initiation and titration of GDMT. We propose a stepped wedge randomized trial to compare the implementation of this model compared to usual care over a 6 month period with 5, 30-day cross over periods. The primary outcome for the trial will be the proportion of patients who have an increase in the number of prescribed evidence-based therapies for HFrEF (beta-blockers, ACE-I/ARB/ARNI, MRA, SGLT2i) 30 days post implementation. This endpoint is based on filling of the prescription. In addition to addition of missing GDMT, we will also consider a change from an ACEI/ARB to an ARNI consistent with increase in the ‘number’ of GDMT given their demonstrated benefit. Secondary outcomes will include: percentage of

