4. STUDY DESIGN

4.1 Study Overview

This is a single ‘center’ (Gallup Service Unit- which includes two ambulatory clinics), stepped wedge cluster randomized design with 5 clusters planned. We will randomize each patient to 1 of 5 clusters, each of which has a different enrollment time point, separated 1 month apart. Each patient will receive intervention with the heart failure care delivery model at time of enrollment. Evaluations will be taken at each cross-over time point and at conclusion of 6 months. Screening data will be reviewed to determine subject eligibility. Subjects who meet all inclusion criteria and none of the exclusion criteria will be entered into the study. Prior to enrollment for each patient, a message will be sent in that patient’s chart through the EHR to the patient’s primary provider who has 7 days to opt out if they think patient should not be enrolled.

Probable Duration of Project: Total duration of subject participation will be 6 months.

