4.4. Randomization

Randomization in this study will occur at the level of the patient. This is a stepped wedge trial design, and patients will be randomized to 1 of 5 clusters. Every cluster will have the model implemented, but the time point of implementation will vary based on cluster, in 30 day increments. Cluster 1 will have the model implemented at time 0, cluster 2 at 30 days, cluster 3 at 60 days, etc (as shown in Figure 1). Prior to implementation, patients in pre-implementation time points will receive usual care. In addition, all providers received a lecture regarding updated ACC/AHA/HFSA guidelines and expert consensus prior to implementation of the model. Given the stepped-wedge design, all patients will eventually benefit from implementation of the model, but it also allows us to evaluate the effect of secular trends towards better care over time (and ensure the model rather than trends in care are not responsible for improving care).

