11.3. Analysis of Primary and Secondary Endpoints

To assess the effectiveness of our intervention, measurement of rates of GDMT, including each specific medication of ACE inhibitors, ARB, ARNI, beta-blockers, MRA, SGLT2 inhibitors will be performed at baseline, at each cross-over time point. The main analysis of our stepped wedge design will be based on a logistic mixed-effects model which will contain a random intercept to account for between-cluster variability, a fixed effect parameter for time, and a group indicator variable for the treatment for each subject and time to capture treatment differences over time.

Safety and tolerability data will be summarized by intervention group.

Adverse event rates will be coded by body system and MedDra classification term. Adverse events will be tabulated by treatment group and will include the number of patients for whom the event occurred, the rate of occurrence, and the severity and relationship to newly started therapy.

Statistical Analysis: The primary analysis will utilize the intention to treat principle. A generalized linear model will be used to assess the relationship between randomization cluster status and the primary outcome. The model will use a log-link and independent correlation structure to allow for calculation of adjusted risk ratios. Statistical significance will be based on a P value of <0.05. For categorical secondary outcomes, a similar generalized linear modeling approach will be used. For continuous secondary outcomes, a generalized linear model will be used.

Assessment of contamination: Providers may learn to better treat heart failure as consistent with evidence-based therapies over time. Given we are not clustering by provider, but rather patients, it is possible that providers will take what is being implemented on their patient that is in an active implementation phase, and apply it to a patient in a non-active implementation phase. Therefore, there is a high risk of contamination. However, with the stepped wedge design, we will be able to also see how GDMT rates increase over the study period for those clusters who are not immediately in an active implementation arm. We will be able to better understand if increases in GDMT are related to the intervention or just due to increases over time due to improved knowledge of providers over time.

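### Class use, doses and mortality at 6 months have no usual-care comparator, yet the analysis plan does not exempt them from comparative modelling, and the 6-month clock is not fixed

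*Combined protocol and SAP*

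**What the plan says.** **Schedule.** Section 4.1: "We will randomize each patient to 1 of 5 clusters, each of which has a different enrollment time point, separated 1 month apart". Section 4.4: "Cluster 1 will have the model implemented at time 0, cluster 2 at 30 days, cluster 3 at 60 days, etc". Section 4.4 adds that every cluster eventually receives the model.

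**Endpoints.** Section 5.2 asks for the percentage on each drug class and the doses, both at 30 days and at 6 months after implementation. It then lists "HF hospitalizations at each time point, 6-month mortality, referrals, cardiac procedures".

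**Analysis.** Section 11.3 relates the primary outcome to the patient's randomized cluster in a log-link generalized linear model, tested at P<0.05. It continues: "For categorical secondary outcomes, a similar generalized linear modeling approach will be used". Continuous secondary outcomes also get a generalized linear model, with no exposure or link named. The synopsis and 11.3 separately describe a logistic mixed model with a cluster intercept, time, and a treatment indicator by subject and time.

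**Where the 6 months start.**
- Synopsis, primary analysis plan: the last measurement is "at the conclusion of 6 months after the implementation of the intervention".
- Section 1: the comparison with usual care runs "over a 6 month period with 5, 30-day cross over periods".
- Section 4.1: "Total duration of subject participation will be 6 months". It gives no starting point, but the same section places the intervention at enrollment.
- Section 4.3: each cluster starts the study under usual care.
- Section 11.3: measurements are listed at baseline and the cross-over points, with no 6-month measurement.

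**The concern.** A stepped wedge gets its randomized contrast from calendar periods in which some clusters are treated and others are not. Once the last cluster has crossed over, that contrast is gone. Three secondary outcomes (class use, doses and mortality at 6 months) are read after that time. The analysis section gives them no treatment of their own, so the general sentence on secondary outcomes applies to them by default.

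Followed as written, the plan could yield risk ratios and P values for 6-month class use and mortality that look like intervention effects but compare start dates among treated patients. Gains in class use or dose at 6 months could also be secular. Section 11.3 itself expects providers' practice to improve over time and calls the risk of contamination high.

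**Working it through.** **1. The plan's own figure.** Section 11.4 states power above 95% for 25% to 50% on one therapy, with four clusters of 20, five time points and 5% type I error (two-sided assumed). With no intracluster correlation and categorical time:
- Variance of a cluster-period mean = 0.375 × 0.625 / 20 = 0.01172.
- With k of 4 clusters treated, a period contributes k(4 − k)/4. For k = 0 to 4 this is 0 + 0.75 + 1 + 0.75 + 0 = 2.5.
- Variance of the effect = 0.01172 / 2.5 = 0.00469, so SE = 0.0685.
- 0.25 / 0.0685 − 1.96 = 1.69, which gives power of 95.5%.

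The figure reproduces. It concerns medication rates within the wedge. No power is stated for any 6-month outcome.

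**2. Timeline.** Inputs: five clusters and 30-day steps from day 0 (4.1, 4.4). The starts at days 90 and 120 extend the stated sequence. Six months is taken as 180 days.

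| Cluster | Start s (= usual-care days) | 6 months after implementation (s + 180) | Treated days by day 180 (180 − s) |
|---|---|---|---|
| 1 | 0 | 180 | 180 |
| 2 | 30 | 210 | 150 |
| 3 | 60 | 240 | 120 |
| 4 | 90 | 270 | 90 |
| 5 | 120 | 300 | 60 |

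Clusters still untreated just after each step: 4, 3, 2, 1, 0. At day 180 and later: 0. The longest usual-care time for any patient is 120 days, so 6-month mortality under usual care is never observed.

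**3. What a model can do with 6-month data alone.** Treatment equals 1 in all five clusters. The treatment column is therefore identical to the intercept, the design matrix has rank 1, and the treatment effect is not estimable. Randomized cluster still varies, but it then indexes start date only.

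**4. Adding an all-treated last period to the longitudinal model.** By the formula in step 1, such a period contributes 5 × (5 − 5)/5 = 0 when observations are independent. With correlation it contributes indirectly, through before/after contrasts within clusters. For five clusters of 20 with one baseline and five steps (linear approximation):

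| Intracluster correlation (assumed) | Within-patient correlation (assumed) | Variance without | Variance with | Reduction |
|---|---|---|---|---|
| 0 | 0 | 0.002930 | 0.002930 | 0% |
| 0.05 | 0 | 0.004576 | 0.004274 | 6.6% |
| 0.10 | 0.5 | 0.002459 | 0.002247 | 8.6% |

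That gain depends on the assumed time trend and on an effect that does not change with time since implementation.

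**5. Outcomes counted over time.** Usual-care time = 0 + 1 + 2 + 3 + 4 = 10 cluster-months. At 20 per cluster that is 200 patient-months, or 6,000 patient-days (16.4 patient-years). Treated time to day 180 = 20 × (180 + 150 + 120 + 90 + 60) = 12,000 patient-days (32.9 patient-years). Usual care is 6,000 / 18,000 = 33%. At N = 80 the two figures are 13.1 and 26.3 patient-years.

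**6. How many deaths this could hold.** The documents give no mortality rate for this population, so annual mortality r of 5% to 20% is assumed. Deaths ≈ patient-days × (−ln(1 − r) / 365.25). At N = 100 this gives 0.8 to 3.7 deaths under usual care and 1.7 to 7.3 under treatment to day 180.

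**7. The clock.**
- From study start: only cluster 1, about 20 of 100 patients, reaches 6 months after implementation by day 180.
- From enrollment, taken as implementation: the endpoint fits exactly, but the 30 to 120 days of usual care in clusters 2 to 5 lie outside the stated participation.
- Covering both takes (s + 180)/30 = 6, 7, 8, 9 and 10 months for clusters 1 to 5.

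**The case against.** The strongest reply has four parts.

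- **No section says that the 6-month outcomes are comparative.** That is so. It is inferred from the general sentence in 11.3, which says similar rather than identical modelling, and for doses names no exposure. Section 11 also promises a detailed SAP. But no other analysis is given for these outcomes and none is labelled descriptive, so the gap stands.
- **The mixed model can include the 6-month measurement as a last period.** This stands for class use. It would be wrong to infer that no model could make any use of these data. The contribution is small and rests on assumptions (step 4), and it is not a concurrent comparison.
- **Most clinical endpoints do have usual-care time.** This stands. A reader might infer that objective 3.2, on differences in HF hospitalizations, reduces to single-arm follow-up. The documents do not support that: the objective covers the study period, and 5.2 measures hospitalizations at each time point. Referrals and procedures have no fixed time point and can use the same period. Section 3.2 does not name mortality.
- **Participation may fit.** A reader might infer that 6 months of participation cannot hold the 6-month endpoints. If participation runs from enrollment, which 4.1 equates with implementation, it holds them exactly. What remains is an unreconciled clock.

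Treating every cluster is a deliberate choice made on ethical grounds and is not criticised here.

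**Conclusion.** The point holds for three outcomes: class use, doses and mortality at 6 months. The number of usual-care patients at that time is 0 on either clock, and no patient has more than 120 days of usual care. The modelling rule in 11.3, applied to 6-month data alone, cannot estimate the intervention effect. This rests on the starts continuing to days 90 and 120. With four clusters, as assumed in 11.4, the last start would be day 90 and the conclusion would be the same.

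It does not extend to HF hospitalizations, referrals or procedures, which have about 10 cluster-months of usual care. The 30-day primary endpoint is outside this point.

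The clock is a separate, smaller matter: the synopsis and Sections 1, 4.1, 4.3 and 11.3 do not settle on one origin, and neither reading of 6 months covers both the control time and the full follow-up in every cluster.

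**What to change.** 1. **Sections 5.2 and 11.3:** report class use, doses and mortality at 6 months as descriptive single-arm results, with estimates and confidence intervals but no intervention P value.
2. **Section 11.3:** base any comparison of deaths and HF hospitalizations on event rates over exposure time, with treatment as a time-varying factor and calendar period in the model. Rely on the periods with concurrent usual care, up to day 120. If later all-treated time is added, state the assumptions on time trend and constancy of effect. Expect few deaths (step 6).
3. **Synopsis and Sections 1, 4.1, 4.3 and 11.3:** reconcile these to one 6-month clock, add the 6-month measurement to 11.3 if it is kept, and state participation as control time plus follow-up.

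The cost is protocol and SAP wording. The downside is that the 6-month secondary results are presented as uncontrolled.

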5.3 Safety Evaluations

Secondary safety endpoints: Secondary safety endpoints include adverse events (to include hypokalemia [$K < 3.0$ mEq/L], hyperkalemia [$K > 5.5$ mEq/L], AKI [defined as Cr increase > 0.5 from baseline], Hyponatremia [$Na < 130$ mg/dL], volume overload [urgent clinic visit/ ER visits for lower extremity edema, dyspnea, with clinical evaluation consistent with volume overload].

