Bradycardia	HR <50 bpm
Urinary Tract Infection (UTI)	Symptoms of UTI and urinalysis/urine culture consistent with infection and/or treated by primary provider for UTI

Candidal vulvovaginitis	Consistent symptoms of infection and/or treated for presumed infection
-------------------------	--

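### The protocol's safety endpoint lists disagree on hypotension and bradycardia, and the hyponatremia limit is written in a unit that would count no events if applied literally

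*Combined protocol and SAP*

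**What the plan says.** The safety events are set out in four places.

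- **Synopsis** (under the secondary endpoints and again under Safety Evaluations): hypokalemia, hyperkalemia, acute kidney injury (AKI), hyponatremia, volume overload, and then "hypotension (SBP <90mmHg), bradycardia (HR <50 bpm".
- **Section 1, Statement of Purpose:** the first five only.
- **Section 5.3:** the list starts "Secondary safety endpoints include adverse events (to include hypokalemia" and its last item closes with "dyspnea, with clinical evaluation consistent with volume overload". It has the same five events as Section 1.
- **Section 10.1, Table 2:** the four laboratory events, hypotension and bradycardia with the synopsis thresholds, and two events found nowhere else, "Urinary Tract Infection (UTI") and "Candidal vulvovaginitis". Volume overload is absent.

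The sodium limit reads "Hyponatremia [Na<130 mg/dl" in the synopsis and "Hyponatremia [$Na < 130$ mg/dL" in Section 5.3. Section 1 and Table 2 give the same figure and unit. Potassium in the same lists is in mEq/L, for example "hypokalemia [$K < 3.0$ mEq/L".

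**The concern.** Section 5.3 is where the body of the protocol defines the safety endpoints, and it is two events shorter than the synopsis. Those two are the ones that home monitoring most directly detects: under Section 7.2 patients receive a home cuff, drugs are added and titrated on home blood pressure, and home blood pressure and heart rate go into the record. No section says which list governs the day-30 safety look or the final tabulation. Section 11 defers detail to a later SAP, whose authors would have to choose between lists, possibly after data have been seen.

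The sodium limit is a separate matter. It is an operative counting rule, and a threshold that no patient could cross makes the hyponatremia endpoint empty if an extraction program applies it as written.

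**Working it through.** The documents give no derived figure to reproduce here. Two checks apply.

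**1. The lists side by side**

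| Event | Synopsis | Section 1 | Section 5.3 | Table 2 |
|---|---|---|---|---|
| Hypokalemia | yes | yes | yes | yes |
| Hyperkalemia | yes | yes | yes | yes |
| AKI | yes | yes | yes | yes |
| Hyponatremia | yes | yes | yes | yes |
| Volume overload | yes | yes | yes | no |
| Hypotension | yes | no | no | yes |
| Bradycardia | yes | no | no | yes |
| Urinary tract infection | no | no | no | yes |
| Candidal vulvovaginitis | no | no | no | yes |
| **Count** | **7** | **5** | **5** | **8** |

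The synopsis contains everything in Section 5.3 plus hypotension and bradycardia; nothing in Section 5.3 is missing from the synopsis. So the conflict between endpoint lists is exactly two events. Section 1 has the same shorter list, so the omission in Section 5.3 does not look like text lost in PDF conversion.

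**2. The sodium unit**

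Inputs: the limit of 130 mg/dL (synopsis, Section 1, Section 5.3, Table 2), and sodium's atomic mass of 22.99 g/mol with valence 1, a physical constant that the documents do not give. So 1 mEq weighs 22.99 mg.

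- The limit as written: 130 mg/dL × 10 dL/L ÷ 22.99 mg/mEq = 56.5 mEq/L.
- The same number in potassium's unit: 130 mEq/L × 22.99 ÷ 10 = 298.9 mg/dL.
- An assumed span of serum values, 110 to 145 mEq/L: 110 × 22.99 ÷ 10 = 253 mg/dL and 145 × 22.99 ÷ 10 = 333 mg/dL.

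Even the lowest assumed value is 253 ÷ 130 = 1.9 times the written limit. Across the whole range, the literal rule counts no events.

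**The case against.** The strongest reply is that little would be lost in practice, and much of it stands.

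- **Collection and reporting.** A reader might infer that hypotension and bradycardia would be missing from the day-30 look and the final report. The documents do not support that. Section 9.1.4 (Adverse Events) captures adverse events throughout, Section 10.1 defines them broadly, and Section 11.3 tabulates them by treatment group without restriction to the Section 5.3 list. The descriptions of the interim look do not refer to Section 5.3 either.
- **Open wording.** The phrase that introduces the list in Section 5.3 can be read as non-exhaustive, and the thresholds for the two events agree wherever they appear. But the synopsis introduces its list in the same way and still names both events, so the open wording does not settle their endpoint status.
- **Table 2 as a rival list.** A reader might count Table 2 as a third endpoint list and report that only four events are common to the synopsis, Section 5.3 and Table 2. That overstates the conflict. Table 2 is introduced as definitions of common side effects of therapy, so it need not match the endpoint list item for item.
- **Sodium.** The unit is the same everywhere and looks like a slip, given the potassium unit beside it. A clinician would probably notice, and if the laboratory reports sodium in mEq/L (an assumption) the harm is small. The limit is still wrong as written.
- **Ascertainment.** A reader might assume that all items are already extracted, so that the change costs nothing. Section 9.1.4 (Vital Signs) takes blood pressure and pulse only from the clinic visit nearest enrollment, and home readings start only once the cuff is given at the intervention time point. Detection may therefore differ between control and intervention periods.

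**Conclusion.** The point holds as a contradiction in endpoint status together with a unit error. Hypotension and bradycardia are prespecified safety endpoints in the synopsis and are not named as such in Sections 5.3 and 1: two events out of the synopsis's seven. They would probably be collected and tabulated as adverse events regardless. What is unsettled is whether they belong to the prespecified safety readout.

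The hyponatremia limit as written is about 56.5 mEq/L and would count no events. That result rests on a literal reading, on sodium's atomic mass, and on assumed serum values of 110 to 145 mEq/L. It does not mean that the trial would in practice record no hyponatremia, since the slip is easy to recognise. The primary endpoint, sample size, power and type I error are not touched.

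**What to change.** 1. Bring Sections 5.3 and 1 into line with the synopsis, so that there is one prespecified safety endpoint list of seven events.
2. Add the volume overload definition to Table 2, so that every endpoint has its definition there. Urinary tract infection and candidal vulvovaginitis can stay in Table 2 as adverse event definitions without becoming endpoints.
3. State that this list is the one used for the day-30 safety look and the final adverse event table.
4. Correct the sodium unit in the synopsis (both entries), Section 1, Section 5.3 and Table 2, with the investigators confirming the intended limit. The AKI creatinine rise of more than 0.5 has no unit in any of these places, and the same edit can supply it.
5. State how blood pressure and heart rate are obtained in control and intervention periods, and say in the report that hypotension and bradycardia may be detected more often after the cuff is given.

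Items 1 to 4 cost wording only. Item 5 costs a sentence in the report, or additional extraction of clinic vital signs during control periods if the investigators want more comparable ascertainment.
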